# **3 INVESTIGATIONAL PLAN**

## **3.1 General Schema of Study Design**

### **3.1.1 Screening Phase**

Potential subjects in the Nephrology, Urology and Spina Bifida outpatient clinics will be screened using the protocol inclusion and exclusion criteria. Those who meet the criteria will be approached by a member of the study team at their regularly scheduled clinic visit or by phone and asked if they would like to hear about the study. If the subject expresses interest, he or she will have an orientation to the WTH platform facilitated by the research coordinator. The research coordinator will help subjects open an account, sign an informed consent, and complete a baseline questionnaire at study entry during a clinic visit. At this enrollment visit, coordinators will explain the bi-directional texting and smartphone adherence reporting to participants and show them how to perform the reporting. Participant phones will be checked to ensure texting and camera capabilities. If a participant does not have a smartphone, a study phone will be provided. Coordinators will also give each participant a Greenfire Clin Card, explaining to the participant how the card works. A member of the Data Coordinating Center (DCC) research staff will activate each card remotely. If participants are pressed for time, they may complete the baseline questionnaires via the WTH platform and will be requested to do so within five days of study entry. Participants who complete their surveys within this time frame will receive \$20. Participants who complete their surveys within 6 – 10 days will receive \$10. They will be sent a text reminder to complete their questionnaires if they have not done so within five days. Coordinators will tell participants that they can earn either a water bottle

---

---

or a phone wallet at baseline for the completion of surveys within this time. They will be given this prize in clinic if they are able to complete all baseline surveys during the clinic visit. If not, they will be mailed their prize.

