### **3.1.2 Run-In and Intervention Phase**

During the first two weeks (run-in period) after questionnaire completion, all participants will be asked to take a photo of their medicines or catheter in hand at the time of treatment without prompts from Way to Health. The photo will be automatically transmitted to WTH and time stamped to record treatment adherence. Coordinators will emphasize that these data will be used to collect baseline information on the routine adherence behavior of AYA with KT and SB, and these data will not be reported to healthcare providers. Participants will receive \$20 (to be administered via Greenfire Clin Card), given as a lump sum at the end of the 2-week period. Participants can track payments in the WTH portal.

After the run-in period, coordinators will call participants to explain the randomization process. Participants will be told that WTH will randomly assign them to one of two groups and will notify them of their status by text. Participants will either be assigned to 1) access personal weekly adherence reports by logging into the WTH website or 2) receive weekly adherence reports automatically to their smartphone with direct feedback on their performance. Participants will also be told that they will receive ongoing weekly compensation for adherence reporting, but that the compensation structure will change and vary by group during the intervention so that we can learn more about the role of financial incentives for AYA.

**Study Arms:** At 2 weeks, a computerized randomization scheme will be generated by WTH to assign participants to one of two arms, stratified by disease group (KT or SB), and age category (12-17 vs. 18-24). User written code in Stata 14.0 will utilize a block randomization scheme that, within each disease/age group stratum stratification, first randomly orders blocks of size 2 and 4 and then randomly orders subjects within blocks. Due to the nature of the study, blinding of participants and research staff is not possible. However, the relying site PI's will

---

---

be blinded. WTH will send a text to each participant explaining the compensation scheme. Participants will be asked to reply yes to confirm receipt and willingness to participate. Additionally, coordinators will call participants at the time to explain the intervention and answer any questions. Subjects will be randomized as follows:

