**Arm 1:** Participants will begin to receive daily text messages as reminders and continue to report real-time treatment adherence with photos. They will receive \$2/week to encourage real-time adherence reporting. Pay is not contingent on meeting a target adherence score, but only on submitting at least one photo per week. In addition to the payments, participants will be able to log in to WTH to see their personal dashboard with a visual display of their weekly adherence performance. They will also be able to access educational resources related to their primary disease. Educational materials for KT recipients will include web links to participant resources specific for AYA, including resources publicly available through the American Society of Transplantation, National Kidney Foundation and the United Network for Organ Sharing and educational videos created by CHOP's care team. The major transplant themes that will be covered include: medication management, infection precautions, energy and physical activity, mental health and social adjustment, nutrition, sexuality and risk behavior education, and vocational resources. Similarly, educational materials for the SB subjects will be drawn from web-based AYA-specific resources, including web links to the Centers for Disease Control Living with Spina Bifida Program and the National Spina Bifida Association. The major SB themes that will be covered include: bladder and bowel management, infection precautions, skin health, physical health, mental health and social adjustment, nutrition, sexuality and risk behavior, safety and vocational resources. All of the educational materials that will be used have been vetted by healthcare professionals, but every resource will be reviewed and adapted by the investigative team to ensure relevance, currency, accuracy and readability. Every month, participants will receive a text encouraging them to visit the WTH educational modules and to check their earnings. WTH is able to track usage of the modules by individual. Parents/legal guardians will have access to these same educational materials via their own WTH portals. Additionally, to mitigate the minimal risk of this study, parents/legal guardians will be notified if their child is excessively non-adherent.

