#### 6.5 Statistical Methods

Clinical and demographic variables will be compared with chi-square or two-sample t-tests for parametric and Fisher's exact or Wilcoxon rank-sum tests for non-parametric data. Treatment groups will be compared with similar analyses to confirm equity in randomization. We will compare change over time in % adherence between arms by fitting quasi-least squares (QLS) and generalized estimating equation (GEE) longitudinal models. The QLS/GEE models include a regression model for the primary outcome variable, in addition to a separate model for the correlation amongst the repeated measures on each subject. The AR (1) correlation structure is plausible because it forces a decline between measures with increasing separation in time; however, we will assess the sensitivity of results to choice of structure. In addition, the models will include treatment group and a time by treatment group interaction. If the interaction term differs significantly from zero, this will indicate that the change over time differs significantly between treatment groups. All analyses will follow the intention-to-treat principle. We will analyze the results for each disease group (SB, KT) separately, although the overall analytical models are the same.

Analysis for Aim 1 and Aim 2 will utilize GEE/QLS models to compare the change over time in the outcome between arms.

For Aim 3, Pearson's or Spearman's Correlations will be calculated to observe the association between outcome and each independent variable.

The statistical analysis will follow the intention-to-treat principle.

---

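### A second willingness check, placed in the payment text that on the natural reading follows allocation, could prompt refusals that differ by arm, and no rule says how refusers are handled

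*Combined protocol and SAP*

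**What the plan says.** The sequence comes from sections 3.1.1 and 3.1.2.

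- **Entry.** Participants "sign an informed consent, and complete a baseline questionnaire at study entry during a clinic visit".
- **Run-in.** Two weeks of unprompted photo reporting.
- **Call.** "After the run-in period, coordinators will call participants to explain the randomization process". In this call they learn that the platform makes the assignment at random and that a text message will give them the result. They also hear that "the compensation structure will change and vary by group during the intervention". Section 3.1.2 mentions no dollar amounts at this call.
- **Allocation at 2 weeks.** The Study Arms paragraph describes the randomisation and then says "WTH will send a text to each participant explaining the compensation scheme". The next sentence reads "Participants will be asked to reply yes to confirm receipt and willingness to participate". Coordinators also telephone at this time to explain the intervention.

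The arm descriptions in 3.1.2 set the pay. Arm 1 receives $2 a week: "Pay is not contingent on meeting a target adherence score, but only on submitting at least one photo per week". Arm 2 gives up that $2 during the intervention and receives $10 in each week in which adherence reaches 85%.

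On analysis, section 6.5 states "All analyses will follow the intention-to-treat principle". Section 6.1 scores an episode without the required photos in the time window as nonadherent. Section 4.5 provides an exit survey for randomised participants who withdraw. No section says what happens to a randomised participant who replies no, or does not reply.

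**The concern.** Randomisation protects the comparison only if the decision to stay does not depend on the arm. Here participants are asked again whether they are willing, and the question is attached to the feature on which the arms differ. A participant who dislikes the terms is invited to say so at that moment.

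Intention-to-treat is stated but cannot repair this alone, because the outcome exists only when photos are sent. A refuser's run-in record can stay in the GEE/QLS model, but the intervention period holds nothing. One option is to leave those weeks missing, in which case the arms are compared among people selected by willingness. The other is to apply the section 6.1 rule and score every episode nonadherent, in which case refusing the study is counted as failing to take treatment. Either route can carry a difference in refusal into the primary result. The plan does not choose between them.

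**Working it through.** **1. The plan's own figures reproduce.** Section 6.6 gives 90 per arm per disease group, alpha 0.05, a difference of 8 points and an SD of 16. Taking the test as two-sided, the normal approximation is Φ(0.5 × √(90/2) − 1.960) = Φ(3.354 − 1.960) = Φ(1.394) = 91.8%; the exact t-test gives 91.6%. Both agree with the stated power above 90%. Enrolment of 180/0.90 = 200 per disease group also agrees.

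**2. What each arm offers over 26 weeks of intervention.**

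- Arm 1: at most 26 × $2 = $52, for one photo a week.
- Arm 2: from $0 to 26 × $10 = $260, according to the number of weeks at 85% or more.
- Comparison: five successful weeks in Arm 2 pay $50, just under the Arm 1 maximum; six pay $60. A participant expecting to reach the goal in five weeks or fewer (5/26 = 19%) could earn more in Arm 1, and anyone expecting more would earn more in Arm 2. Either offer can disappoint.

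**3. Lost numbers are not the main problem.** Take 100 randomised per arm, effect 8, SD 16, and assumed losses in the two arms (normal approximation):

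| Loss, one arm / other arm | Power |
|---|---|
| 15% / 5% | 91.8% |
| 20% / 10% | 90.2% |
| 30% / 10% | about 88% |

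**4. Refusers kept and scored nonadherent.** Shift in the arm difference = (difference in refusal) × (adherence level the refusers would otherwise have had). The documents give neither quantity; both are assumed.

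| Difference in refusal | Level 50% | Level 80% |
|---|---|---|
| 3 points | 0.03 × 50 = 1.5 | 0.03 × 80 = 2.4 |
| 5 points | 0.05 × 50 = 2.5 | 0.05 × 80 = 4.0 |

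This is 1.5 to 4.0 points, or 1.5/8 = 19% to 4.0/8 = 50% of the planned difference, in favour of the arm with fewer refusals.

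**5. Refusers left out.** Suppose those who stay would change by D points more than those who refuse, with the same D in both arms. The mean among stayers then exceeds the full-arm mean by D × (refusal rate), so bias = D × (difference in refusal). With D assumed at 8 to 16, a 3 to 5 point difference gives 0.03 × 8 = 0.24 to 0.05 × 16 = 0.8 points. As an outer case, 5% against 15% refusal gives 0.8 to 1.6 points and raises the two-sided type I error from 5% to between 6.3% and 10.3%. If refusers would have done worse, this bias favours the arm with more refusals, the opposite of step 4. The handling rule therefore decides the direction as well as the size.

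**6. Scale.** Steps 4 and 5 use mean adherence, the scale on which the 8 points appear to be set. Section 6.1 defines the primary outcome as the change in the proportion of weeks at 85% or more. The formulas carry over, but the levels and SD on that scale are not given, so the figures are indicative only.

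**The case against.** The reply is not the first agreement to take part. Signed consent, a completed run-in and a call saying that pay varies by group all come earlier, and section 8.6 requires participants to read a full description of the study. The consent form is not in the available copy, so amounts may already have been disclosed. A reader might infer that participants agree only once they know their arm; the documents do not support that.

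Nor do they state that one text reveals both the allocation and that arm's pay. Section 3.1.2 says status is notified by text and, separately, that a text explains compensation, and this comes before the sentence introducing the two arms. A post-allocation, arm-specific message is the natural reading, but it is an inference.

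A reader might also infer that Arm 1 will lose more people and that the result will tilt towards Arm 2. Step 2 shows why this does not follow: Arm 2 pays nothing in a week below 85%, so poor adherers may prefer Arm 1. Nothing in the plan says that non-repliers are excluded.

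There are safeguards. Staff telephone at allocation and contact anyone silent for more than three days (3.1.4, 4.4), 10% drop-out is allowed for (6.6), and those lost to follow-up are to be compared with completers (2.4, 6.4). Participants cannot be blinded and may leave at any time, so rewording one text will not stop all arm-related attrition.

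These points limit the claim but do not remove it. The drop-out allowance is one rate for both arms, the comparison with completers is not planned by arm, and none of the safeguards says how a refuser is analysed.

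**Conclusion.** The concern holds as a risk built into the procedure. Participants are asked for willingness a second time, in a message about pay that most naturally follows allocation, and the handling of a missing or negative reply is unspecified. Differential refusal is possible but not shown: the documents give no refusal rate, and its direction cannot be predicted from the payment rules.

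The 1.5 to 4.0 point shift rests on an assumed 3 to 5 point difference in refusal, an assumed adherence level of 50% to 80%, scoring of refusers as nonadherent, and the mean-adherence scale. It shows that a small imbalance could matter beside an 8-point target; it does not estimate bias in this trial. The change is worth making because the step can be moved at almost no cost.

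**What to change.** 1. In the existing call after the run-in, describe both arms, ask whether the participant is willing to accept either, and randomise only those who agree.
2. Make the post-allocation text a confirmation of receipt only, and state in 3.1.2 whether it follows allocation and whether it gives the participant's own scheme.
3. State in 4.5 and 6.5 that a missing or negative reply does not remove a randomised participant from follow-up or analysis unless they formally withdraw, and that those who withdraw remain in the intention-to-treat set. Say whether their intervention weeks are treated as missing or as nonadherent, and prespecify the other choice as a sensitivity analysis.
4. Report non-replies and withdrawals by arm.

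The cost is a script change and a few sentences in the protocol, with no extra contact. A few participants may decline before randomisation, which slightly affects recruitment and generalisability but not the comparison. Describing both schemes in advance may also make disappointment with the allocated arm more likely. The change removes a prompted exit, not all attrition.

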### **3.1.3 Follow-up Phase**

Six months after randomization, participants will receive a message that the main study intervention is ending but that we will continue to track their adherence reporting to understand the benefits of the study. At this time, all participants and parents/legal guardians will repeat the baseline questionnaires. Arm 1 will continue to receive reminders and report their daily adherence with mobile phone camera photography and earn \$2/week for reporting, but they will no longer have access to their WTH portal, i.e. no visualization of dashboard or educational modules. Arm 2 will be told that incentives will be tapered. They will no longer be able to access the WTH portal. Arm 2 participants will get \$2/week for reporting during this follow-up period and will continue to receive weekly adherence feedback texted to them. They will be eligible to receive an additional \$10 for meeting their adherence target of  $\geq 85\%$  over a lengthened time interval. Specifically, they will receive feedback and \$10 every 2 weeks x 4 (if goal is met over average of preceding 2 weeks), then \$10 every month x 2 (if average monthly goal is met) then no incentive (beyond the \$2/week for reporting) for the last two months. At the end of the follow-up phase, participants and parents/legal guardians, again, will complete the baseline questionnaires. Participants who complete their surveys within 5 days will receive \$20. Participants who complete their surveys within 6 – 10 days will receive \$10.

Parents/legal guardians will no longer have access to their WTH portal during this phase, but will still receive messages if their child is excessively non-adherent.

### **3.1.4 Study Staff Involvement**

Beyond enrolling and helping set up WTH portals, coordinators and/or study staff will phone participants at the time of randomization, at the end of six months and end of follow-up period to answer any questions. Coordinators and/or study staff will also contact participants if they fail to report adherence for more than 3 days in a row to assess barriers, such as technical

---

---

issues, etc. The DCC research staff will pay participants monthly by uploading earnings to their Clin Cards. Research staff will confirm the participant has possession of his/her Clin Card prior to loading the card with the money earned

### **3.2 Allocation to Treatment Groups and Blinding**

Subjects will be randomized to Arm 1 or Arm 2 via a computerized randomization scheme generated by WTH to assign participants to one of two arms, stratified by disease group (KT or SB), and age category (12-17 vs. 18-24). User written code in Stata 14.0 will utilize a block randomization scheme that, within each disease/age group stratum stratification, first randomly orders blocks of size 2 and 4 and then randomly orders subjects within blocks. Lead investigators at each site will be blinded to which Arm their participants are in. The research staff must know which participants are in which Arm in order to appropriately manage each participant.

### **3.3 Study Duration, Enrollment and Number of Sites**

#### **3.3.1 Duration of Study Participation**

The study duration per subject will be 12.5 months, with a 2-week run-in, 6-month intervention and 6-month follow-up.

#### **3.3.2 Total Number of Study Sites/Total Number of Subjects Projected**

The study will be conducted at CHOP, Boston Children's Hospital, Children's Healthcare of Atlanta, Seattle Children's Hospital, Lurie's Children of Chicago, and Children's Mercy. CHOP will act as the DCC.

We will recruit 3 cohorts. Cohort one and two are the KT and SB subjects, respectively. Cohort three is the parent/legal guardian(s) of those enrolled in cohort one and two. Recruitment will stop when 200 total subjects are recruited in both cohort one (KT) and cohort two (SB), respectively. It is expected that approximately 400 subjects will be enrolled between the two cohorts to produce 180 evaluable KT and 180 evaluable SB subjects. Approximately 50 KT and 50 SB participants will be recruited at each of the four centers. Recruitment for cohort 3 will stop when 800 parent/legal guardian(s) are recruited. Recruitment of the parent population will be dependent upon the recruitment of cohorts one and two. Up-to 200 parents/legal guardians may be recruited at each of the four centers.

### **3.4 Study Population**

Subjects 12 to 24 years of age and their legal parent/guardian(s) will be recruited from the Nephrology, Urology and Spina Bifida clinics at CHOP, Boston Children's Hospital, Children's Healthcare of Atlanta, Seattle Children's Hospital, Lurie's Children of Chicago, and Children's Mercy.

#### **3.4.1 Inclusion Criteria**

- 1) Males or females age 12-24 years.
  - 2) KT subjects must be greater than 3 months post-transplant.
  - 3) SB subjects must be able to perform CIC as part of their treatment.
-

- 
- 4) Able to speak and read in English.
  - 5) Willing and able to provide informed assent or consent.
  - 6) Parental/guardian permission (informed consent) if appropriate.

### **3.4.2 Exclusion Criteria**

- 1) Unwilling to participate.
- 2) Unable to speak or read in English.
- 3) Unable to provide informed assent or consent.
- 4) Severe cognitive impairment, as reported by treating team in recruiting clinic.
- 5) On dialysis
- 6) Acquired post-transplant lymphoproliferative disease less than one year prior to enrollment
- 7) Less than 3 months post-transplant.
- 8) Unable to perform CIC.
- 9) Prescribed Immunosuppressive medications once per day.
- 10) Provider recommendations of CIC once per day

Parents/legal guardians meet the inclusion criteria if their child is eligible for the study. Parents/legal guardians will be excluded if they meet one or more of items #1-4 of the above exclusion criteria. Subjects that do not meet all of the enrollment criteria may not be enrolled. If a subject's parent is unwilling to participate, the subject may still enroll in the study. In this case, clinical information about the parent, such as household income and education level, will not be collected. Any violations of these criteria must be reported in accordance with IRB Policies and Procedures.

## **4 STUDY PROCEDURES**

### **4.1 Screening Visit**

Using the WTH web-based research portal, a research coordinator will help subjects and their parents/legal guardians open an account, electronically sign an informed consent and complete a baseline questionnaire. The baseline questionnaire will include the surveys listed in section 5.2.1 Diagnostic Tests, Scales, Measures, etc. as well as a general demographics questionnaire. The coordinator will explain the WTH portal, and set-up text reminders with the participant's input.

